3.3 End of Study

The end of study is defined as either the date of the last visit of the last subject to complete the [REDACTED] Safety Follow-up, or the date of receipt of the last data point from the last subject that is required for primary or secondary analysis, as pre-specified in the protocol and is subject to provisions in [Section 3.2](#), whichever is the later date.

4 STUDY POPULATION

4.1 Number of Subjects

It is anticipated that approximately [REDACTED] subjects who participated in prior studies of ozanimod in CD (RPC01-2201, RPC01-3201, RPC01-3202, RPC01-3203) will be eligible for treatment in this study.

4.2 Inclusion Criteria

Subjects must satisfy the following criteria to be enrolled in the study:

[figure not shown]
1. Subjects who are not in clinical response and/or clinical remission after completing 12 weeks in the Induction Studies RPC01-3201 or RPC01-3202, subjects who experience relapse in the Maintenance Study RPC01-3203, subjects who complete the Maintenance Study RPC01-3203, subjects who complete at least 1 year of RPC01-2201.
2. Subject should not have any constraints under local regulations, must provide written informed consent prior to any study-related procedures, and must have the ability to comply with the [REDACTED]
3. Female subjects of childbearing potential (FCBP):

Note: For the purposes of this study, a female subject is considered to be of childbearing potential if she 1) has not undergone a hysterectomy (the surgical removal of the uterus) or bilateral oophorectomy (the surgical removal of both ovaries) or 2) has not been postmenopausal for at least 24 consecutive months (that is, has had menses at any time during the preceding 24 consecutive months).

Must agree to practice a highly effective method of contraception throughout the study until completion of the [REDACTED] Safety Follow-up Visit. Highly effective methods of contraception are those that alone or in combination result in a failure rate of a Pearl Index of less than 1% per year when used consistently and correctly. Examples of acceptable methods of birth control in the study are the following:

- combined hormonal (containing oestrogen and progestogen) contraception, which may be oral, intravaginal, or transdermal
- progestogen-only hormonal contraception associated with inhibition of ovulation, which may be oral, injectable, or implantable
- placement of an intrauterine device (IUD)
- placement of an intrauterine hormone-releasing system (IUS)
- bilateral tubal occlusion
- vasectomized partner
- complete sexual abstinence

Periodic abstinence (calendar, symptothermal, post-ovulation methods), withdrawal (coitus interruptus), spermicides only, and lactational amenorrhoea method are not acceptable methods of contraception. Female condom and male condom should not be used together.

4.3 Exclusion Criteria

[figure not shown]
The presence of any of the following will exclude a subject from enrollment:

4.3.1 Exclusions Related to General Health:

1. Subject has any clinically relevant cardiovascular (See [REDACTED] hepatic, neurological, pulmonary [severe respiratory disease (pulmonary fibrosis or chronic obstructive pulmonary disease)], ophthalmological, endocrine, psychiatric, or other major systemic disease making implementation of the protocol or interpretation of the study difficult or that would put the subject at risk by participating in the study. In France, hypotension is exclusionary if it makes the implementation of the protocol or interpretation of the study difficult or would put the subject at risk by participating in the study.
2. Subject is pregnant, lactating, or has a positive urine beta human chorionic gonadotropin (β -hCG) test.
3. Subject has suspected or diagnosed intra-abdominal or perianal abscess that has not been appropriately treated.

4.3.2 Exclusions Related to Medications:

[figure not shown]
4. Hypersensitivity to active ingredients or excipients of ozanimod

[figure not shown]

[figure not shown]
4.3.3 *Exclusions Related to Laboratory Results and Other Assessments:*

8. Subject has any clinically significant abnormal results (eg, labs or ECG) which, in the opinion of the Investigator, may put the subject at risk.
9. Subjects has a pre-dose resting [REDACTED]. One recheck is allowed at the Day 1 visit. If [REDACTED] remains [REDACTED] at Day 1, one additional recheck is allowed at a later date within the available window for roll-over from the previous study.

[figure not shown]

[figure not shown]
6 PROCEDURES

6.1 Treatment Period

Visits, assessments, and procedures will be performed as per the [REDACTED]
[REDACTED] instructions for missed doses are in [Section 7.2](#).

6.1.2 Pre-Baseline Assessments/Day 1 Visit

For these at-risk subjects, the duration of the visit on Day 1 will be approximately 7 hours.

See [APPENDIX B](#) for further SARS-CoV-2 guidance.

6.1.3 Study Visits

Visits, assessments, and procedures will be performed according to [REDACTED]

Subjects who have previously received ozanimod for at least 1 year in an open-label study such as RPC01-2201 do not return for visits at [REDACTED].

6.1.5 Study Stopping Rules

The sponsor has the right to terminate the study for safety reasons. In addition, the sponsor may terminate the study for administrative reasons. In all cases, all necessary measures have to be taken to guarantee appropriate safety follow-up of all subjects already included in the study.

The Institutional Review Board (IRB) or Independent Ethics Committee (IEC) and the Regulatory Authorities will be informed in writing about any termination of the study.

6.3 Efficacy Assessments

See [Section 2](#) for a description of study endpoints.

6.3.1 *Crohn's Disease Activity Index*

The CDAI is a composite score that is used to measure the clinical activity of CD. The CDAI uses a questionnaire with responses scored numerically and weighted. Scores range from 0 to approximately 600, with higher scores indicating greater disease activity. The 8 components used to assess the CDAI and their weighting factors are noted in [Table 3](#). The definitions of mild, moderate, and severe CD are provided in [Table 4](#).

Subject-reported components of the CDAI (stool frequency and abdominal pain components and general well-being) will be collected in an electronic diary. Subjects will complete their electronic diary starting at Pre-baseline visit and will continue throughout the study.

Subjects will be instructed on the use and completion of questions on the electronic diary.

The diary entries will be reviewed by site personnel during pre-baseline and throughout the study.

Table 3: Crohn's Disease Activity Index Assessment

Clinical or Laboratory Variable	Weighting Factor, \times
Number of liquid or soft stools each day for 7 days	2
Abdominal pain (graded from 0-3 on severity) each day for 7 days	5
General well-being, assessed from 0 (well) to 4 (terrible) daily for 7 days	7
Presence of complications ^b	20
Taking diphenoxylate/atropine, loperamide, or opiates for diarrhea	30
Presence of an abdominal mass (0 as none, 2 as questionable, 5 as definite)	10
Hematocrit 47-HCT in men and 42-HCT in women	6
Percentage deviation from standard weight	1
Total Score	

Abbreviations: HCT = hematocrit.

^b One point each is added for each set of complications: arthritis or arthralgia; iritis or uveitis; erythema nodosum, pyoderma gangrenosum, aphthous stomatitis; anal fissure, fistula or perirectal abscess; other bowel-related fistula; febrile (fever) episode over 100 degrees during the past week.

Table 4: Crohn's Disease Severity Definitions

Severity	CDAI Score
Mild	150-219
Moderate	220-450
Severe	> 450

Abbreviations: CDAI = Crohn's Disease Activity Index.

6.3.2 Simple Endoscopic Score for Crohn's Disease

The SES-CD assesses the degree of inflammation. The SES-CD assesses the following four components: size of ulcers, ulcerated surface, affected surface, and presence of narrowing. Each of these components are scored on a scale of 0 to 3 as outlined in [Table 5](#).

In the SES-CD, each of these 4 components are assessed in the 5 segments of the ileum and colon: ileum, right, transverse, left (descending and sigmoid), and rectum. The SES-CD is the sum of the individual scores of each of the components across the 5 segments.

Endoscopic response has not yet been validated and may be defined as a 25% to 50% or greater decrease in SES-CD from baseline. Endoscopic remission has not yet been validated and may be defined as SES-CD \leq 4 points and a SES-CD decrease \geq 2 points, an absence of large ulcers, absence of ulcers, or SES-CD = \leq 2.

To ensure quality data and standardization, the same endoscopist and the same diameter colonoscope as used in screening should be used throughout the study wherever possible.

Colonoscopies will be read at a centralized reading facility in a process outlined in the Endoscopy Image Charter. Centralized reading will be the primary assessment for endoscopy; local endoscopy scores will also be collected. Biopsies are not required in this study.

Table 5: Definitions of Simple Endoscopic Score (SES-CD) for Crohn's Disease

Variable	SES-CD Values			
	0	1	2	3
Size of ulcers	None	Aphthous ulcers (0.1 to 0.5 cm)	Large ulcers (0.5 to 2 cm)	Very large ulcers (>2 cm)
Ulcerated surface	None	<10%	10%-30%	>30%
Affected surface	Unaffected segment	<50%	50%-75%	>75%
Presence of narrowings	None	Single, can be passed	Multiple, can be passed	Cannot be passed

6.3.3 Abdominal Pain and Stool Frequency

The abdominal pain and stool frequency scores are based on 2 components of the CDAI ([Khanna, 2015](#)). See [Section 6.3.1](#) above for more details.

Stool frequency and abdominal pain, as described in [Section 6.3.1](#), will be obtained and calculated without a weighting factor for use as part of the inclusion criteria. These unweighted subject-reported assessments will also be used as efficacy endpoints ([Section 2](#)).

6.4 Other Assessments

6.4.1 Physical Examination

A complete physical examination will be performed to evaluate the heart, lungs, head and neck, abdomen, skin, extremities, and weight as well as to check for visual symptoms (eg, blurred vision or decreased visual acuity as reported by the subject). A full examination of the skin should be repeated every 24 weeks. An interim physical examination will include weight and a check for visual symptoms, and an evaluation of body systems with previously noted abnormalities and/or those body systems associated with any new complaints from the subject. See [\[REDACTED\]](#) for additional details and [\[REDACTED\]](#)

6.4.2 Vital Signs

Systolic and diastolic blood pressure and pulse will be assessed in a supine and standing position at every visit. An automated validated device may be used, if available. In case the cuff sizes available are not large enough for the subject's arm circumference, a sphygmomanometer with an appropriately sized cuff may be used. Subjects entering from a blinded study and deemed as high risk due to cardiac conditions will be carefully monitored after the first dose of investigational drug with a 6 hour post-dose monitoring period of hourly recording of pulse and blood pressure as described in [\[REDACTED\]](#)

6.4.3 *Electrocardiogram*

The 12-lead digital ECG devices will be provided to each clinical site by the central ECG laboratory for the duration of the trial. Detailed instructions describing the process for recording and transmission of the digital ECGs will be outlined in the trial-specific manual and provided to the site before the start of the trial. Paper versions of ECG tracings will be printed and photocopied to preserve the ink if necessary and kept at the site as source documentation. An ECG will be performed while resting. Electrocardiograms will be performed before the first dose of IP in all subjects and 2, 4, and 6 hours after the first dose of investigational drug administration for at-risk subjects (as outlined in [REDACTED] or in all subjects if deemed necessary by national or local requirements, on Day 1 while the subject is in the clinic.

All ECGs will be evaluated by the treating physician, with input from a local cardiologist (upon approval from a Medical Monitor) or a central reader to confirm if additional monitoring is required. If a local cardiologist is not available upon discharge, discharge criteria was evaluated by the treating physician, and the central results are assessed as abnormal or unmeasurable then the subject will need to return for further evaluation.

[REDACTED] Only clinically significant abnormalities should be reported in the medical history/current medical conditions or the AE electronic case report form (eCRF).

[figure not shown]
At the [REDACTED] Safety Follow-up Visit, an ECG should be repeated if the ECG at the ET/EoT visit shows a new abnormal result.

6.4.4 *Pulmonary Function Tests*

The pulmonary function test (PFT) refers to “pulmonary function test – no bronchodilator” (eg, spirometry which includes total and timed vital capacity, and expiratory flow rate measurement). [REDACTED]

Pulmonary function tests may be performed at a qualified pulmonary function laboratory, respiratory department, or at the clinical trial site. If being performed at the clinical trial site, the Principal Investigator may delegate the performance of this test to any staff member that is qualified to perform the pulmonary function test. If the pulmonary function test results are not within normal range and are considered clinically significant, the results must be verified by a pulmonologist, and potential confounding factors identified. Please refer to the American Thoracic Society / European Respiratory Society guidelines for standardization of spirometry and single breath determination of carbon monoxide uptake in the lung (MacIntyre 2005; Miller 2005a; Miller 2005b).

[REDACTED]

7 DESCRIPTION OF STUDY TREATMENTS

7.1 Description of Investigational Product(s)

Ozanimod capsules will be manufactured, quality control tested, and released in accordance with Good Manufacturing Practices (GMP).

Ozanimod will be provided as powder-filled capsules. Ozanimod drug substance is blended with microcrystalline cellulose, colloidal silicon dioxide, croscarmellose sodium and magnesium stearate in opaque hard-gelatin capsules. Ozanimod doses and strengths are expressed as the HCl salt form of ozanimod. Two ozanimod dosage strengths have been prepared for the clinical investigations: 0.23 mg (size 4 capsule; equivalent to ozanimod HCl 0.25 mg) and 0.92 mg (size 4 capsule; equivalent to ozanimod HCl 1 mg).

The capsules will be orally administered singularly, or in varying combinations, to achieve the desired dose for clinical studies.

There is no provision for dose adjustments in this study. Subjects who cannot tolerate IP must be withdrawn from the study.

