3 OVERALL STUDY DESIGN

3.1 Study Design

This is a Phase 3, open-label, multicenter extension study to evaluate safety and explore the long-term efficacy of ozanimod 0.92 mg in subjects with moderately to severely active CD. It is anticipated that approximately [REDACTED] subjects who have participated in a prior study of ozanimod for CD will be eligible to participate in this study if they meet the eligibility criteria and have not met the discontinuation criteria as outlined in the prior studies (eg, RPC01-3201, RPC01-3202, RPC01-3203, and RPC01-2201).

Subjects entering the study from RPC01-2201 will continue to receive ozanimod 0.92 mg/day (equivalent to ozanimod HCl 1 mg). Subjects entering the study from RPC01-3201, RPC01-3202, or RPC01-3203 will initiate ozanimod treatment in accordance with a 7-day dose escalation regimen as follows:

- Days 1 through 4: Ozanimod 0.23 mg daily (equivalent to ozanimod HCl 0.25 mg)
- Days 5 through 7: Ozanimod 0.46 mg daily (equivalent to ozanimod HCl 0.5 mg) (administered as two 0.23-mg capsules)
- Day 8 through End of Study: Ozanimod 0.92 mg daily (equivalent to ozanimod HCl 1 mg)

Subjects who discontinue from treatment due to lack of response, AEs, or other reasons, even if alternative treatment is given, will be followed for [REDACTED] for collection of safety data, including lymphocyte recovery, and for assessment of their disease status. Refer to [REDACTED] and [Section 11.1](#) for further details on lymphocyte recovery monitoring.

The study will be conducted in compliance with the International Council on Harmonisation (ICH) of Technical Requirements for Registration of Pharmaceuticals for Human Use/GCP and applicable regulatory requirements.

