14 DISCONTINUATIONS

14.1 Treatment Discontinuation

The following events are considered sufficient reasons for discontinuing a subject from the IP(s):

- AE
- withdrawal by subject
- death
- lost to follow-up
- lack of efficacy
- pregnancy

The reason for discontinuation of treatment should be recorded in the eCRF and in the source documents.

The decision to discontinue a subject from treatment remains the responsibility of the treating physician, which will not be delayed or refused by the sponsor. However, prior to discontinuing a subject, the Investigator may contact the Medical Monitor and forward appropriate supporting documents for review and discussion.

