14.2 Study Discontinuation

Subjects may voluntarily withdraw from the study at any time. The Investigator will provide a written explanation in the source documentation to be entered on the appropriate eCRF page describing the reason for discontinuation.

[figure not shown]
The criteria for enrollment are to be followed explicitly. If a subject who does not meet enrollment criteria is inadvertently enrolled, the Medical Monitor must be contacted, and that subject will be withdrawn from the study if continuation is determined to be a safety risk.

Reasons for discontinuation include, but are not limited, to the following:

- Physician decision: The Investigator must discontinue IP if it is determined that it is not safe or in the subject's best interest to receive further treatment. The Medical Monitor should be promptly notified of the decision.
- Noncompliance with IP: After consultation between the Investigator, the Medical Monitor, and the sponsor when appropriate, a subject may be discontinued from the study for failure to comply with dosing regimen as specified by the protocol.
- Noncompliance with protocol/protocol deviation: After consultation between the Investigator, the Medical Monitor, and the sponsor when appropriate, a subject may be discontinued from the study for failure to follow protocol procedures, or other event or decision that stands in contrast to the guidelines set in the protocol.
- AE: A subject must be discontinued from IP if, in the judgment of the Investigator or if specified in the protocol, the subject develops an AE such as an intercurrent illness or complication that justifies discontinuation of IP.

- Lack of efficacy: Decision by the subject and/or the Investigator to discontinue IP due to a lack of expected or desired effect related to a therapy.

- Withdrawal by subject: The subject may choose to discontinue IP at any time. Every effort should be made within the bounds of safety and subject choice to have each subject complete the End of Treatment Visit and [REDACTED]. If a subject withdraws consent, the only additional investigational data to be collected will be the follow-up of SAEs as mandated by the protocol.
- Pregnancy: If a female subject becomes pregnant, IP must be discontinued ([Section 12](#)).
- Study termination by sponsor
- Other

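### Section 7.1 withdraws intolerant subjects from the study, whereas Section 3.1 keeps subjects who stop treatment for adverse events in follow-up; Section 14.2 does not settle which applies

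*Combined protocol and SAP*

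**What the plan says.** Section 7.1 (Description of Investigational Product(s)) explains that doses cannot be adjusted in this study and then adds: "Subjects who cannot tolerate IP must be withdrawn from the study". It mentions no follow-up for these subjects.

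Section 3.1 (Study Design), repeated in the Protocol Summary, sets the rule for people who come off the drug: "Subjects who discontinue from treatment due to lack of response, AEs, or other reasons, even if alternative treatment is given, will be followed for" a redacted period, "for collection of safety data, including lymphocyte recovery, and for assessment of their disease status".

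Section 14.1 (Treatment Discontinuation) lists an adverse event among the reasons for stopping the product. Section 14.2 (Study Discontinuation) opens its own list with "Reasons for discontinuation include, but are not limited, to the following", and the adverse event entry reads: "A subject must be discontinued from IP if, in the judgment of the Investigator or if specified in the protocol", with a reference to an event that justifies stopping. That entry says nothing about what happens next. The two noncompliance entries in the same list speak of discontinuation from the study instead. The only visible wording about a closing visit is in the entry on withdrawal by the subject: "Every effort should be made within the bounds of safety and subject choice to have each subject complete the End of Treatment Visit".

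Section 9.5 (Subject Disposition) sets a minimum list that counts those who complete the study and those who do not, by reason. It has no separate line for stopping the product while remaining in follow-up.

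**The concern.** Long-term safety is the first part of the study objective in Section 2.1. Subjects who cannot tolerate the drug bear directly on that objective, and what happens to them after the last dose is part of the evidence.

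Stopping the product and leaving the study are different events with different consequences for data. Section 7.1 uses the second term for a group that Section 3.1 treats under the first. A site that reads Section 7.1 literally could close the subject's participation before the follow-up described in Section 3.1 takes place. The missing data would not be a random sample: they would come only from subjects who did badly on the drug. Those subjects would also miss the monitoring that Section 3.1 describes for them.

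**Working it through.** No arithmetic in the plan bears on this point. There is no powered sample size, no hypothesis test and no assumed dropout rate to reproduce, so the check is a comparison of wording.

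**Step 1: do the two rules cover the same subjects?** Section 3.1 applies to anyone who stops treatment for lack of response, adverse events or other reasons. Intolerance that ends treatment falls within that class. Section 7.1 applies to the same people.

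**Step 2: are the rules compatible?** Section 7.1 requires withdrawal from the study. Section 3.1 requires continued follow-up within it. Both are mandatory in form. No visible text says that a subject withdrawn under Section 7.1 remains in the Section 3.1 follow-up.

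**Step 3: does Section 14 resolve it?** Section 14.1 and the adverse event entry in Section 14.2 both refer to stopping the product, which leans towards Section 3.1. But the Section 14.2 entry stands under a study discontinuation heading, in a list that also contains departures from the study, and has no follow-up instruction of its own. Section 14.2 therefore adds to the ambiguity.

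**Step 4: which data would be exposed if Section 7.1 were applied literally?**

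- *Serious events: largely protected.* Sections 10.1.2 and 13 require reporting within a redacted number of days counted from the last dose, whatever the subject's study status. Sections 10.2.6 and 13 require follow-up of serious events still open when participation ends.
- *The intolerance event itself: captured.* It arises on treatment and is tabulated under events leading to discontinuation (Section 9.7).
- *Non-serious events after the last dose: exposed.* Section 10.1.2 records all adverse events through the close of safety follow-up, which presumes that the subject enters that period.
- *Lymphocyte recovery and disease status: exposed.* Both are named purposes of the Section 3.1 follow-up.
- *Repeat ECG: exposed.* Section 6.4.3 calls for it at a safety follow-up visit when the early termination or end-of-treatment tracing is newly abnormal.

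**Step 5: direction.** The definition of treatment-emergent events in Section 9.7 gives no end date, so post-dose events in follow-up would count. Losing some of them can only lower the event counts. If patient-years of exposure means time on drug (the visible text does not define it further), the denominator would not shrink with them, so exposure-adjusted rates would also fall. For lymphocyte recovery and disease status the documents do not fix a direction. Those summaries would simply rest on a group that excludes some intolerant subjects.

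**Step 6: size.** Let *p* be the proportion of subjects who stop for intolerance and *q* the proportion of those who are handled under the literal wording of Section 7.1. The proportion of all subjects with curtailed follow-up is *p × q*, and within the intolerant group it is *q*. The documents give neither value. The sample size and follow-up length are redacted as well, so no estimate can be derived.

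**The case against.** The strongest reply is that the protocol, read as a whole, does not let early departure end follow-up. Section 3.1 is as binding as Section 7.1, is the specific rule on post-treatment follow-up, names adverse events, and holds even when another treatment is started. Section 7.1 is a remark in a product description, made to explain that there is no lower dose to fall back on. Section 6.4.3 links a safety follow-up visit to an early termination visit, so such visits are expected after early termination. Section 14.2 cuts data collection back to serious events only when consent is withdrawn, and an investigator stopping the drug for intolerance is not that. Section 10.1.2 makes no exception for intolerant subjects. Finally, the visit schedule and parts of Sections 3.1 and 14.2 are redacted or not shown, and may hold clearer instructions.

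Much of this stands, and it rules out several stronger readings that a reader might infer:

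- *That Section 14.2 clearly stops the product and keeps follow-up.* Its adverse event entry does not mention follow-up. Section 3.1 is the only firm counter-passage.
- *That intolerant subjects would lose the whole safety follow-up.* Serious events remain reportable and are followed, and the event that led to stopping is already recorded.
- *That everyone affected had a drug-related event.* The documents do not equate intolerance with suspected causality.
- *That a particular percentage of subjects is affected.* Any figure would be one assumption multiplied by another.

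What the reply does not do is remove the conflict. It depends on sites setting aside an explicit requirement in Section 7.1 in favour of text elsewhere. Further wording in redacted passages would leave that requirement as it is.

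**Conclusion.** The contradiction between Sections 7.1 and 3.1 is real and visible in the text, and Section 14.2 leaves it open. It is an inconsistency of wording. The documents do not show that any data have been or will be lost.

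The harm is conditional on a site applying Section 7.1 literally, and it is bounded. It covers non-serious events after the last dose, lymphocyte recovery, safety follow-up assessments such as the repeat ECG, and disease status, all confined to intolerant subjects. Where it occurred, adverse event summaries would tend to look more favourable. Its size cannot be computed from the documents.

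The conclusion assumes that intolerance leading to a stop falls within the Section 3.1 class, and that no redacted text overrides Section 7.1. The point should be corrected, because it touches the study's main objective and the correction is small.

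**What to change.** Reconcile Section 7.1 with Sections 3.1, 14.1 and 14.2:

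- Define discontinuation of the product and withdrawal from the study as separate terms, and use them consistently in all four sections.
- State for each term which data collection continues, so that the wording of Section 7.1 does not by itself end the follow-up already planned in Section 3.1.
- In Section 14.2, separate the reasons for stopping the product from the reasons for leaving the study, or label each entry.
- In Section 9.5, count the two separately by reason, and show how many subjects who stopped the product completed the safety follow-up. That would let a reader see how much post-treatment information is missing and from whom.

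The treatment rule itself is for the sponsor to settle. The cost is one sentence in Section 7.1, consistent terms in Section 14, and extra lines in the disposition summary. The case report form may need a matching field if it does not already record the two statuses separately; the documents do not describe it. No visits are added, because the follow-up is already planned.
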